### **Phase II**

**2. To assess preliminary outcomes of the ESTIMA HIV Prevention Program** Using a two-armed randomized controlled design, we will recruit FSW (n=120, 60 in each arm) who will be randomized to: 1) the ESTIMA intervention (gender equity program and *Via* microfinance program) or 2) a wait-list control group. Women will be part of groups of approximately 10 women each, and each group will be randomized to intervention or control conditions. At 12 months follow-up, we hypothesize that compared to control participants, intervention participants will have: **a)** Significantly greater economic security (e.g. decreased debt, increased income, decreased number of sex trades) and **b)** Significantly greater perceived collective power (i.e. collective efficacy) to address gendered power imbalances within social structures and the community.

**3. To assess feasibility regarding all aspects of implementation, receptivity by participants and staff, and capacity to be maintained by *Via* microfinance efforts** Qualitative focus groups (n=2 or less per intervention group, 10 women per session), individual interviews (approximately 5 per intervention group), and quantitative assessments will be conducted with intervention participants, along with staff feedback via post-training evaluation forms, to inquire about satisfaction with and appropriateness of the program, as well as aspects pertinent to the ethical conduct of the intervention. We will also monitor recruitment, random assignment, adherence to intervention design, retention of participants, contamination across arms, and the incidence of adverse events.

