Monitoring and evaluation of recruitment, random assignment, adherence to intervention design, retention of participants, contamination across arms, and the incidence of adverse events will include: 1) standard training and periodic observations for all intervention staff; 2) weekly meetings between intervention staff and the Program Director, in which intervention staff review difficult situations that have arisen and discuss these and possible solutions; and 3) quantitative data collection on program recruitment, delivery (e.g. whether all segments of the curricula were covered), potential contamination (e.g. number of control participants who report knowing women in the ESTIMA intervention) and retention. A final report will be developed based on this review to provide future recommendations regarding best approaches for program implementation as well as appropriateness of the intervention content.

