### **15. RISK MANAGEMENT PROCEDURES AND ADEQUACY OF RESOURCES**

Minimizing Psychological risks and distress. The use of trained and sensitive staff will minimize embarrassment or discomfort among participants during the survey or interview. The Research Director and PI will work closely with research staff to ensure there is close oversight, support, and monitoring of the data collection process. Research staff conducting all interviews will clarify at consent all requirements of confidentiality from all individuals, staff and participants,

involved in this study. Due to greater risk for psychological stress rather than physical risk from this largely behavioral study, we have undertaken additional precautions to minimize emotional distress to participants. Survey or interview participants who become emotionally distressed will be reminded that they can skip any questions they prefer not to answer, that the survey or interview can be stopped at any time. The facilitator will stay alert for any signs that the participant is becoming emotionally distressed by the survey or interview. At the conclusion of the survey or interview, all participants will be screened for emotional distress in the following way: "These questions can make some people feel sad, anxious, or angry. How are you feeling now?" At study entry, participants will be clearly informed through the consent process that they may terminate their participation at any point.

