b. Responsible Entities: In each research site, project staff will report emotionally distressed participants to the site manager (a physician) who will be responsible for ensuring the FSWs mental health care. The site manager will refer the participant to the clinic's on-site psychologist. The project staff, and clinical coordinator at each research site will be responsible for immediately reporting any breaches of protocol, breakdowns in the consent process, violations of confidentiality of the data, complaints by participants or any serious problems or adverse events to the on-site manager who will file an incident report with [name] at the Tijuana General Hospital and to Drs. [name]/[name] at the University of California, San Diego. Procedures for these events will be outlined in a manual (described below). Any ethical issues relevant to the research protocol and consent process will be discussed during regular staff meetings with the PI and research staff. Furthermore, we have incorporated an evaluation of the ethical conduct of the study within the process evaluation of our study (see Aim 3 above). Supervisory staff will be trained to monitor any issues related to breaches of confidentiality and any complaints by participants will be brought to the attention to supervisory staff as well as the PI of both the parent study and the ESTIMA study. In turn, Drs. [name]/[name] will make an incident report to the SDSU IRB and the Human Research Protection Program. The IRB in San Diego will report to NIDA and DHHS if warranted. Requests for the use of these data by persons outside of the project will be decided upon by the PI, [name] and a committee comprised of U.S. and Mexican co-investigators. The IRB board will be informed, and any concerns will be addressed before data are released.

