c. Policies and Procedures: A policies and procedures manual for the project will specify immediate data monitoring and response. Participants will be informed during the consent procedure that confidentiality may be breached under certain circumstances. In cases where a breach of confidentiality is necessary, project staff will be instructed to report to the on-site manager who will file an incident report with Drs. [name] and [name] and [name] (Mexico) within 24 hours. The incident report requires a detailed account of the problem, date of occurrence, date it came to the PI's attention, impact on participant, and corrective action taken. An investigation will occur in both Mexico and San Diego. In San Diego, the SDSU IRB will make a determination if the event was related to research, directly or indirectly, and, if so, require revisions of protocol or consent, as applicable, and re-review of these procedures by the IRB, with copies to the Office of Human Subjects for any necessary further action.

Project staff at each research site will be required to obtain certification from the Tijuana General Hospital so that they are aware of the type of adverse events that may warrant a breach of confidentiality. Monitoring of potential adverse events or serious problems will be given high priority by project staff and researchers. For example, any participant who is seriously depressed and threatening to harm herself will be immediately interviewed by the on-site manager and appropriate treatment or referral will be immediate; clinics have an on-site psychologist. All such potentially adverse events or serious problems would be reported within 24 hours on a standard form to the SDSU IRB with a copy to the Office of Human Subjects. All project staff will receive verbal and written instructions pertaining to the rules governing the maintenance of confidentiality upon completion of the study or if they leave the study before its completion.

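### Adverse-event incidence is to be monitored under Aim 3, but no scheduled source common to both arms is designated to supply it, so incidence compiled as written would depend on programme contact

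*Combined protocol and SAP*

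**What the plan says.** Section 6 (Phase II, third aim) lists what will be monitored, including "contamination across arms, and the incidence of adverse events". Section 9, under Specific Aim 3, repeats the list and names three activities:

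- The conduct of the programme is covered by "standard training and periodic observations for all intervention staff".
- Problems met along the way are taken to "weekly meetings between intervention staff and the Program Director, in which intervention staff review difficult situations that have arisen".
- Counts come from "quantitative data collection on program recruitment, delivery (e.g. whether all segments of the curricula were covered), potential contamination", with retention listed as well.

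Outside Aim 3, Section 16 (Data Safety Monitoring and Adverse Event Reporting) makes site staff report "complaints by participants or any serious problems or adverse events to the on-site manager who will file an incident report". It adds: "Monitoring of potential adverse events or serious problems will be given high priority by project staff and researchers". Sections 15 and 16 give a 24-hour limit for reports to the IRB. These rules cover all participants, but they start only when something reaches staff.

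Some assessments are common to both arms. Section 15 states: "At the conclusion of the survey or interview, all participants will be screened for emotional distress in the following way". Section 9 describes one survey at baseline, 6 and 12 months, given by interviewers who do not know the assignment. It covers violence by several kinds of perpetrator, debt and number of sex trades. HIV/STI tests are done at baseline and 12 months. The analysis paragraph in Section 9 treats violence, HIV risk and HIV/STI as longer-term outcomes and describes no summary of adverse events.

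**The concern.** An incidence needs a numerator found in the same way for everyone in the denominator. Here the activities named for the numerator sit mainly with programme staff. Controls do not enter the programme until after the 12-month assessment, so programme staff have no planned occasion during follow-up to learn of an event in a control.

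The harms at issue are ones the protocol itself foresees. Sections 14 and 16 describe a woman becoming known as a sex worker through taking part, and violence or harassment if that happens. Section 14 also describes others taking the loan money. The first two can occur in either arm, because controls also enrol, attend the study office and are traced through contacts.

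The pilot is meant to support a full-scale trial. If harms are counted mostly where staff are present, a higher count in the ESTIMA arm could reflect closer observation alone, and an excess among controls could stay hidden.

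**Working it through.** The documents state no adverse-event rate or target, so there is no figure to reproduce. The check sets each possible source against three questions.

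| Source (section) | Reaches both arms? | Scheduled? | Named as an adverse-event source? |
|---|---|---|---|
| Training and observation of intervention staff (9, Aim 3) | No | Periodic | Yes, as part of the monitoring list |
| Weekly intervention-staff meetings (9, Aim 3) | No | Yes | Yes, as part of the monitoring list |
| Quantitative data on recruitment, delivery, contamination, retention (9, Aim 3) | Yes in part (contamination is asked of controls) | Yes | Adverse events not among the contents |
| Incident reports (15, 16) | Yes | No | Yes, as reporting only |
| Distress screen after each survey (15) | Yes | Yes | No |
| Violence, debt, sex trades in the survey (9) | Yes, interviewers blinded | Yes | No |
| HIV/STI tests (9, 20) | Yes | Baseline and 12 months | No |

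No row has a clear yes in all three columns.

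Can the common assessments serve as they stand?

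- **Distress screen.** It asks how the woman feels now, after the questions. It does not ask about events since the last visit.
- **Violence items.** They record acts by perpetrator and are usable for occurrence. Section 14 excludes violence unrelated to the protocol from research-related adverse events, and no described item makes that link.
- **Exposure, harassment after exposure, money taken.** Neither the outcome measures nor the survey domains in Section 9 describe such items. The supplemental discrimination scales may overlap with harassment but are not described as covering it after disclosure.

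Other monitoring also leans to the programme arm. The post-training staff forms and the satisfaction interviews (Section 9), the loan-repayment monitoring (Section 15) and the close watch on each ESTIMA group for loss of confidentiality (Section 16) all concern women in the programme.

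**Illustration of the effect.** Inputs: 60 per arm (Section 6). Assumed, not in the documents: true risk 20% in both arms, detection 90% in ESTIMA, detection *s* in controls. Expected observed events = 60 × true risk × detection.

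- ESTIMA: 60 × 0.20 × 0.90 = 10.8
- Controls, *s* = 0.90: 60 × 0.20 × 0.90 = 10.8; ratio 1.0
- Controls, *s* = 0.60: 60 × 0.20 × 0.60 = 7.2; ratio 10.8 / 7.2 = 1.5
- Controls, *s* = 0.30: 60 × 0.20 × 0.30 = 3.6; ratio 10.8 / 3.6 = 3.0

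The true risk cancels, so the ratio is 0.90 / *s* whatever the risk.

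**The case against.** The strongest reply is that much harm is already measured fairly. The distress screen, the blinded survey and the tests apply to both arms and cover several loan-related harms foreseen in Section 14, such as more clients, violence and HIV/STI exposure. This stands. A reader might infer that nothing scheduled collects events in the same way in controls, and the documents do not support that.

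Four further points:

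- **No arm comparison of adverse events is promised.** Aim 3 speaks of monitoring within a feasibility aim, and no adverse-event test is planned. This stands. It would be wrong to treat incidence as a declared trial outcome. But an incidence from a two-arm study will be read by arm, and this one could not bear that reading.
- **Women who leave the programme are not lost.** Section 9 plans to track programme drop-outs as well as loss to follow-up, so one should not infer that leavers go unseen. What is missing is an item to ask them.
- **Contact counts do not give a size.** A reader might set about 16 weekly payments (2,875 / 179.69 = 16.0) against a control's two follow-up visits. Section 9 does not say that a payment is a staff contact. Controls also have locator-update visits (Section 11), a 24-hour telephone line (Section 12), and results visits with outreach to those who do not return (Sections 9 and 20). Contacts are not detection probabilities in any case.
- **The documents are not the whole record.** The Aim 3 list is introduced as what monitoring will include, new survey items may follow from Aim 1, and the final survey and the procedures manual are not shown. So the finding is that no such item or designation is described, not that none will exist.

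**Conclusion.** The point holds as a gap in designation and content. Aim 3 promises to monitor adverse-event incidence, the activities it names either see one arm or do not mention adverse events, and the safety reporting is spontaneous. Scheduled measures common to both arms exist but are not assigned to this purpose, and three kinds of foreseen harm have no described item.

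Incidence compiled as written would therefore depend on programme contact and would not be comparable by arm. The size cannot be derived from the documents. The ratios of 1.5 and 3.0 rest on assumed detection of 90% against 60% and 30% with equal true risk, and show only that unequal detection could by itself look like harm from the programme. Greater detection in the ESTIMA arm is expected from its greater contact but is not demonstrated.

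This is a worthwhile, cheap correction. It does not touch the primary intermediate outcomes or the power statement.

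**What to change.** 1. Add a few identical items to the 6- and 12-month surveys for all randomised women, including those who left the programme. Ask whether each event occurred since the last visit: others learning of her sex work, harassment or violence after that, and money taken or controlled by others. Ask about occurrence only. Women know their arm and controls hold no study loan, so asking a woman to attribute an event to the study would bring back a difference between arms. Relatedness can stay with the IRB determination already described in Section 16.
2. State in Aim 3 that incidence by arm comes from these items, the existing violence items and the HIV/STI results. Give the number of women assessed in each arm as the denominator, because at the planned 80% retention only 60 × 0.80 = 48 per arm would have a 12-month survey.
3. Keep all spontaneous and staff-reported events, list them separately, and do not compare them between arms.

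The cost is a slightly longer survey at visits already planned and a short addition to Aim 3. The wording must avoid mention of the loan or the group, so that answers do not reveal the arm to the interviewer.

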## **10. HUMAN SUBJECTS**

The proposed mixed methods study will be paired with a 5-year study led by [name] (R01 DA028692) that aims to explore the spatial dimensions of HIV risk among FSW in Tijuana. This parent study has recruited 400 FSW (18 or older using venue based sampling), with quantitative assessment at 6, 12 and 18 months follow-up. Recruitment and follow-up for the ESTIMA study will coincide with the follow-up periods of the parent grant. The baseline data collection for the parent grant will be used to recruit for formative research of ESTIMA (Aim 1), and the 12 and 18 months follow-up of the parent grant will coincide with the ESTIMA baseline and 6 month follow-up (Aim 2).

### **Characteristics of the sample**

We anticipate that female participants will range in age from 18 to 48 years (mean approx. 31); mean level of educational attainment will be 7 years; 5% will be illiterate; 67% will be single; 87% will have children; 30% will be from Central America; and 70% will be of Mexican origin.

Eligibility criteria for the current study include:

- Biologically female,
- At least 18 years old,
- Ability to Speak English or Spanish
- Report having agency over their earnings (i.e. women that do not have pimps, brokers, or others who may try to take control over the money and/or women's business initiation)

- No reported use of marijuana on a daily basis or more and no reported use of other hard drugs (i.e. heroin, cocaine, crystal, crack, amphetamines, etc.) weekly or more
- Report having exchanged sex for money, goods, shelter or drugs within the last month,
- Live in Tijuana or its suburbs and have no plans to permanently move over the next 18 months
- Willing and able to provide informed consent
- Agree to receive antibiotic treatment for Chlamydia, gonorrhea and syphilis if they test positive
- Not be a part of a recent behavioral intervention (*Mujer Segura* or *Mujer Más Segura*).

For Phase 1 (Aim 1), women from the parent study (n=30) (see recruitment details below) who report interest in becoming participants in the ESTIMA intervention (Specific Aim 2) will be contacted to participate. Additional eligibility will include: having no plans to move in the immediate year, and having no issues with cognitive impairment that may interfere with their decisions to participate in the ESTIMA Project (see section 26).

For Phase 2 (Aims 2-3), using a two-armed randomized controlled design, we will recruit FSW (n=120, 60 in each arm) from the parent study as well as via venue-based sampling methods similar to the parent study if needed (i.e. if we do not obtain sufficient numbers from the parent study to recruit) who will be randomized to: 1) the ESTIMA intervention (gender equity program and Via microfinance program) or 2) a wait-list control group. Women will be part of groups of approximately 10 women each, and each group will be randomized to intervention or control conditions. We will recruit ESTIMA participants from those who are completing 12 month follow-up for the parent study, using the same eligibility criteria and recruitment in Specific Aim 1 (assessing interest among those who indicate willingness to be recruited into this study), with an additional criteria related to women's drug use frequency; the specific criteria will be determined based on Aim 1 findings, consultation from the CAB and Via microfinance (drug use data will be retrieved from the parent survey; 41% and 53% report using drugs and alcohol less than once per week respectively). Those who participated in Aim 1 and who fall within these drug-related eligibility criteria are also eligible for participation. Research staff of ESTIMA and the parent grant will work jointly to identify those willing and eligible during the 12 months follow-up data collection of the parent grant, and explain the ESTIMA study to further assess interest. If we do not obtain at least 120 participants from the parent study we will conduct additional recruitment following the same recruitment protocol as the parent study (MAPA de Salud, PI: [name], protocol 100148).

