## 6. SPECIFIC AIMS

We aim to develop, implement, and evaluate a program called *ESTIMA* (Economic and Social empowerment To Increase upwards Mobility Among women), which translates to “valuing myself” in Spanish. ESTIMA is a program that will incorporate gender equity content into an existing microfinance program, Our microfinance partner, *Via International* (*Via*), which has provided microloans in Tijuana since 1999, provides over \$200,000 in microloans yearly. *Women’s Empowerment International* (WEI), which has sponsored over 9300 microloans to women in Mexico, will provide the capital for *Via* to expand their microfinance program for the proposed ESTIMA program, and has a long history in sponsoring business training and microfinance programs in Latin America and elsewhere. Economic vulnerability is a critical factor in heightening risk for HIV among FSW and this combined program addresses such vulnerability while also supporting women via community mobilization to address both economic and social burdens.

The specific aims include:

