Via International, which will implement the microfinance program along with the community mobilization, has provided microfinance loans in Tijuana since 1999, providing over \$200,000 in microloans yearly. Women's Empowerment International, which will be providing the capital for the loans, has sponsored over 9300 microloans to women in Mexico, and has a long history in sponsoring business training and microfinance programs in Latin America and elsewhere. Facilitation will be by the *Via* training team, who will be trained on gender equity community mobilization strategies. Priorities of mobilization efforts will be identified by the ESTIMA collectives, facilitated by the election of collective leaders, and guided by the findings of Aim 1. Notably, our preliminary work in this area (communication with FSW involved in ongoing UCSD research projects) indicate that women are very interested in ESTIMA; many women reported that they initiated sex work to save money to start a business. Women will be provided with a loan of up to \$2,500 pesos each. (See Appendix I for details on the ESTIMA program, see also section 15 for managing risks associated with taking out loans). Women are required to repay the loan within 4 months at 15% interest, which means paying back a total of \$2,875 pesos or the equivalent which is a payment of \$179.69 pesos per week for 4 months: \$23.44 pesos fee for the loan per week as interest and \$156.25 pesos to pay back the loan. The loans are at a standard flat rate of 15% over the course of 4 months. While we recognize that this is high, this is lower compared to other existing programs in Mexico, (e.g. Comportamos, which is the largest microfinance program in Mexico, provides loans at higher rates), and is consistent with microfinance programs abroad, including the program from which the ESTIMA project is modelled, called IMAGE: Intervention with Microfinance for AIDS and Gender Equity. The IMAGE project in South Africa offers loans at a flat rate of about 14% (personal communication with [name], project director of IMAGE). IMAGE was successfully implemented and produced significant reductions in partner violence as well as HIV risk behaviors among women in South Africa, and has been sustained and scaled up for the past 6 years to reach over 25,000 women.

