appointments. Screening questions include age, agency over earnings, engaging in exchange of sex for money, drugs, goods or shelter; date of last exchange; intention to move in the next year, drug use, and debt. We will add a few non-related 'red herring' questions (e.g. marital status, place of work) to prevent women from guessing eligibility criteria. Screening will take place in a confidential area where the potential participant feels safe to answer freely.

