*Risks associated with taking out a microfinance loan:* Our microfinance partner, Via Microfinance, provides over 300 loans a year to poor women in Tijuana to support them to start a business. The repayment rates are 90% or greater. If women need more time to pay loans back, they will be able to work with the lender to develop a schedule for paying the loans back. Loans that are not paid in full, even in cases when more time is provided for pay-back, will result in higher interest charges on subsequent loans to the group or denial of requests for subsequent loans. If a participant defaults on repayment, they will face high interest rates if they proceed to take out more loans. We do not expect that the initial \$2,500 pesos will be difficult for women to repay. Women may also use sex work to supplement their income if they are having trouble paying these loans back as well, which could increase the frequency of their sex trades. To address these issues, Via microfinance will support women on all aspects. Via has a strong record for supporting women in their microfinance groups and they have extremely high rates of repayment. Via has the capacity to work with women to manage their repayment schedules as well. Finally, women can choose to take out less than the \$2,500 pesos amount if they feel concerned and they can take out more as they see fit (after they pay back the initial loan). Women may also fear that pimps, male partners, or others may learn of their involvement in this program and try to take the loan money away from them or require that they use the money for some other purpose. To further address these risks, we will include these issues in our formative work in Aim 1, Phase I interviews and we will also consult our community advisory board as we prepare to initiate the ESTIMA program. We will be able to recruit women who do not report pimps and who report having control over their money earned (e.g. women who do not report having to give some portion of their salary to brokers or pimps), based on responses to items in the quantitative survey (from the MAPA de Salud study). Finally, we will address this issue during study initiation, trainings, and upon provision of the loan money to women. We will encourage women not to discuss their study involvement and access to this loan money with others, especially with pimps, brokers, or others who may try to take control over the money and/or women's business initiation. Notably, only 4% of women from the study sample reported having pimps or managers who make money from their earnings. We will also monitor the repayment on these loans closely. By staggering these groups over time, we will also be able to alter the program in ways to best address this issue over time (i.e. if this is an issue at all for the first group of 6, we will implement changes to address this prior to initiating the next group of 6). Given that *Via* has had over a decade of experience working with poor women in Tijuana and providing loans, they have experience in helping women develop schedules for paying these loans back.

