Risks and Protections related to Stigma and Confidentiality within the group setting among FSW. Women's confidentiality will be prioritized, in terms of providing information and specimen samples to research staff, but also in terms of their participation in a group among FSW. Particular items in the formative interviews will focus on women's comfort and willingness to participate in a group setting with other FSW. In such a setting, women will identify themselves as conducting sex work. We will ensure that the group understands that they must keep the participation in this group confidential, as some women may not want others in the community to know about their work as sex workers. We will take all steps and efforts to ensure that women's safety is not jeopardized in this group setting. The formative work (phase I, specific aim 1) will be helpful for guiding this process. We have found that in the formation of other sex work collectives, while some women prefer to remain "secret" sex workers and participate in the collective confidentially, others are excited to engage in rallies, trainings, or conferences for FSW – making their identity as a sex worker known within the community. While women will be recruited who would be *willing to be part of a group of FSW* training in microfinance and supporting each other in a collective group, we will also take necessary steps to ensure all women's comfort and safety in the program by prioritizing confidentiality.

Notably, the *Via* Microfinance program currently serves women vulnerable to GBV and HIV, but who are not necessarily FSW. Thus, this program is not recognized in the community as a program that serves FSW. We will take further efforts to ensure that in no way is the *Via* program ever recognized as such by the community; this will be critical to ensure women's safety, confidentiality, as well as success in their new businesses. Every effort will be made to ensure women's confidentiality in terms of her status as a sex worker, her participation in the study, as well as any of the data collected as part of such study participation.

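### Neither the eligibility criteria nor the contamination measure covers women who hold an ordinary Via loan or training, which is the economic half of ESTIMA

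*Combined protocol and SAP*

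**What the plan says.** Section 6 describes the intervention as an addition to something already running: "ESTIMA is a program that will incorporate gender equity content into an existing microfinance program". Section 9 names the provider: "Via International, which will implement the microfinance program along with the community mobilization, has provided microfinance loans in Tijuana since 1999". Section 15 says that the lender "provides over 300 loans a year to poor women in Tijuana to support them to start a business". Section 16 (Phase II) says that the "program currently serves women vulnerable to GBV and HIV, but who are not necessarily FSW".

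The eligibility list in section 10 contains one exclusion for earlier programme exposure, "Not be a part of a recent behavioral intervention", followed by the names Mujer Segura and Mujer Más Segura. The screener in section 9 is described this way: "Screening questions include age, agency over earnings, engaging in exchange of sex for money, drugs, goods or shelter". It then adds the date of last exchange, plans to move, drug use and debt. Neither place mentions Via, other microfinance lenders or business training.

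Under Specific Aim 2 and in section 11, wait-list women receive referrals and standard care, and are offered ESTIMA after the 12-month assessment. Neither text addresses a Via loan taken in the meantime.

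Contamination across arms is to be monitored under Aim 3. The one indicator given is "potential contamination (e.g. number of control participants who report knowing women in the ESTIMA intervention". Separately, the survey described in section 9 for use at 6 and 12 months asks whether the woman is in debt and to whom.

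**The concern.** The comparison is meant to set Via's loans and training plus gender-equity mobilisation against neither. Via's part can be had outside the trial. The criteria are silent on it, so a current or recent Via client can meet all of them and be assigned to the wait-list. Controls are also free to borrow from Via while they wait. By section 19 they are women interested in microfinance, and by section 12 the programme is fully described to them at consent.

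A control in either position already has the component expected to move income, debt and number of sex trades. Those are among the outcomes on which the trial is powered. Collective power is affected less, because it is the target of the mobilisation content, which ordinary Via clients are not said to receive. Prior clients are spread over both arms by randomisation, so the expected consequence is dilution toward zero.

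The second cost falls on Aim 3. A control with her own Via loan who knows nobody in ESTIMA would add nothing to the stated indicator. The pilot could then report a weak economic effect beside a low contamination count, and both results are meant to inform a larger trial.

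**Working it through.** **1. The plan's own power figure.** Inputs from section 9 (power calculations): 60 per arm with 80% retention, so 60 × 0.80 = 48; effect 0.5 SD; alpha 0.05, sidedness not stated; stated power 80%. The formula is power = Φ(d√(n/2) − z), with d√(n/2) = 0.5 × √24 = 2.449.

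- One-sided: 2.449 − 1.645 = 0.804, power 78.9%.
- Two-sided: 2.449 − 1.960 = 0.489, power 68.8%.

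The one-sided value is close to the stated 80%. A two-sided test comes close only with no dropout (60 per arm, 78.2%), or with ANCOVA and a baseline correlation of about 0.49, which the documents do not state. Both versions are carried below. Like the plan, this treats women as independent.

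**2. Dilution.** Let c be the share of women with Via exposure outside the trial and f the share of the full effect that such exposure carries. Neither is in the documents. Exposed controls already have the part f, so d = 0.5 × (1 − c·f). For women who were clients before entry, this covers both arms: in that stratum ESTIMA adds only 1 − f, and 0.5 × [(1 − c) + c(1 − f)] = 0.5 × (1 − c·f). No further term is needed for prior clients in the intervention arm.

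**3. A scale from the documents.** Section 15 gives just over 300 loans a year and section 7 about 9,000 sex workers in Tijuana. If every loan went to a different sex worker, 300 / 9,000 = 3.3%, or 2 of 60 controls. Via lends to poor women generally and repeat loans are possible, so for sex workers at large this is an extreme reading. It ignores that trial entrants are selected for interest in microfinance.

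**4. Results at 48 per arm.**

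| c | f | d | Power, one-sided | Power, two-sided |
|---|---|---|---|---|
| 0 | – | 0.500 | 78.9% | 68.8% |
| 3.3% | 0.5 | 0.492 | 77.8% | 67.3% |
| 3.3% | 1 | 0.483 | 76.5% | 65.9% |
| 10% (assumed) | 0.5 | 0.475 | 75.2% | 64.3% |
| 10% (assumed) | 1 | 0.450 | 71.2% | 59.7% |
| 20% (assumed) | 1 | 0.400 | 62.4% | 50.0% |

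At 3.3% with f = 1 the loss is 78.9 − 76.5 = 2.4 points one-sided and 68.8 − 65.9 = 2.9 points two-sided.

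**5. What the creditor question can see.** As described, it concerns debt at the time of the survey. Section 9 gives a 4-month repayment term, and assessments are 6 months apart. A loan on that term, taken in the first 6 − 4 = 2 months after a visit and repaid on schedule, is gone by the next visit. The question does not cover business training, and no eligibility, contamination or analysis rule uses the answer.

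**The case against.** The best opposing case is that overlap is possible but not shown. No passage reports a sex worker or parent-study participant who borrows from Via, and section 16 says that Via is not known locally as a programme for sex workers. On the documents' own figures the share looks small. The rationale in section 7 is that economic help alone may fall short, which argues against f = 1. The survey already asks about creditors in both arms, so a loan outstanding at a visit can be seen. The Aim 3 indicator is introduced as an example, so other measures are not excluded. Comparing ESTIMA with ordinary community access to credit is also a legitimate contrast, in a pilot that says it may only find trends.

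Most of this stands as a limit on size. It does not supply a rule on Via exposure, and the creditor question misses repaid loans and training. If ordinary access is the intended comparison, that access still has to be measured to be described.

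A reader might infer more than the documents support:

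- That the plan deliberately admits Via clients, or that controls are known to be exposed. They are admitted only by silence, and no exposure is reported.
- That the list screens out another HIV programme while letting this one through. The documents call Mujer Segura only a behavioural intervention.
- That the contrast falls to 0.40 SD. That needs a 20% share and full effect, and neither has a source.
- That Aim 3 could not detect the problem. The indicator is an example, and the creditor question gives partial information.

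Section 9 refers to an appendix for programme details. It is not in the text available here, so Via's own enrolment rules could not be checked.

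**Conclusion.** The gap is real and its likely size is modest. Via exposure outside the trial is not addressed at entry, is not restricted or specifically tracked during the wait, and would be missed by the one contamination indicator named. The effect is dilution toward zero, mainly in income, debt and sex trades.

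The only scale that can be built from the documents is about 3.3%, which takes 0.5 SD to about 0.48 and costs roughly 2 to 3 points of power. It assumes that every Via loan goes to a different sex worker and that such a loan carries the whole effect. Selection for interest in microfinance could raise the share, and the 10% and 20% rows are illustrations only. The unstated sidedness of alpha matters more for power (78.9% against 68.8%). The stronger reason to act is that the Aim 3 contamination result cannot otherwise be interpreted for the economic component.

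**What to change.** - **Entry.** Add one criterion to section 10 and one matching screener item: not a current or recent borrower or trainee in a Via loan group, with the look-back period stated. Ask it of every entrant, including those coming from the parent study.
- **Follow-up.** At 6 and 12 months in both arms, use the existing creditor question and add one item on any microfinance loan or business training since the last visit. That interval catches loans already repaid. Word it identically in both arms and place it after the outcome questions: the wording will not signal the arm, but an answer might.
- **Reporting.** Report the result by arm as an Aim 3 contamination measure beside the count of controls who know ESTIMA women. In the intervention arm, separate the ESTIMA loan and training from any other.

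The cost is one screener item, one survey item and the loss of a few otherwise eligible women. Self-report is enough, so no names need go to Via. Borrowing during the wait would be measured, not prevented.
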